10.5 Relationship to Trial Treatment

The assignment of the causality should be made by the investigator responsible for the care of the participant using the definitions in Table 4: Definitions of Causality.

If any doubt about the causality exists the local investigator should inform the trial coordination centre who will notify the Chief Investigators. In the case of discrepant views on causality between the investigator and others, the MHRA will be informed of both points of view.

Table 4: Definitions of Causality

Relationship	Description
Unrelated	There is no evidence of any causal relationship. N.B. An alternative cause for the AE should be given
Unlikely	There is little evidence to suggest there is a causal relationship (e.g. the event did not occur within a reasonable time after administration of the trial medication). There is another reasonable explanation for the event (e.g. the participant's clinical condition, other concomitant treatment).
Possibly	There is some evidence to suggest a causal relationship (e.g. because the event occurs within a reasonable time after administration of the trial medication). However, the influence of other factors may have contributed to the event (e.g. the participant's clinical condition, other concomitant treatments).
Probably	There is evidence to suggest a causal relationship and the

	influence of other factors is unlikely.
Almost certainly	There is clear evidence to suggest a causal relationship and other possible contributing factors can be ruled out.

10.6 Expectedness

All events judged by the Chief Investigator or delegate to be possibly, probably, or almost certainly related to the flucloxacillin, graded as serious and **unexpected** (see Reference Safety Information described in section 10.3.1) for list of Expected Adverse Events) should be reported as a SUSAR. The assessment of expectedness will not be assessed by the reporting investigator; this will be determined by the chief investigator or their delegate.

10.7 Follow-up After Adverse Events

All adverse events should be followed until satisfactory resolution or until the investigator responsible for the care of the participant deems the event to be chronic or the participant to be stable.

When reporting SUSARs the investigator responsible for the care of the participant should apply the following criteria to provide information relating to event outcomes: resolved; resolved with sequelae (specifying with additional narrative); not resolved/ongoing; ongoing at final follow-up; fatal or unknown.

10.8 Reporting Procedures

Regardless of treatment arm, complications (AEs) will be reported for participants where the event is deemed serious and the causal relationship to flucloxacillin is assessed and judged by the investigator to be possibly, probably or almost certainly related to flucloxacillin. Depending on the nature of the event the reporting procedures below should be followed. Any questions concerning reporting should be directed to the coordinating centre in the first instance. If the trial treatment ends prematurely, participants will be followed up until trial end.

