3.3 Risk:Benefit

CF START will assess the withdrawal of an intervention (flucloxacillin prophylaxis) that has been a routine component of UK CF care for over 40 years.

Flucloxacillin is licensed for this age group, has a clear safety profile and is used widely in the UK as a specific therapy for acute infection with SA. Use of flucloxacillin as a prophylactic antibiotic is standard care for infants with CF, but is unusual outside of this indication.

Flucloxacillin treatment is very rarely associated with an increased risk of hepatic disorders, namely, hepatitis and cholestatic jaundice. (6). These reactions are related neither to the dose nor to the route of administration of flucloxacillin, and reported cases were mainly in those >50 years of age. There are no reports in infants or children with CF despite being a routine component of UK CF care for over 40 years.

For infants randomised to “*Prevent and Treat*”, the risk relates to earlier acquisition of infection with *PsA*, an outcome that the trial is designed to assess.

For infants randomised to “*Detect and Treat*”, the risks relate to earlier infection with SA and the potential impact of this on respiratory condition. Again we will be collecting important secondary outcomes assessing the impact on respiratory condition, including the measurement of lung clearance index at 40-48 months. As such we aim to provide a clear result that assesses the safety and efficacy of both of these strategies.

Infants randomised to “*Detect and Treat*” may receive less antibiotic therapy than is appropriate for standards of care. This will be addressed through the training of site staff and by working in partnership with families. Parent/carers will be provided with multi-media resources to support understanding of the trial and be empowered to provide appropriate care working with their CF team. Empowering and working in partnership with parent/carers is standard CF practice, but will be reinforced for the trial, in light of the potential risk to infants in the “*Detect and Treat*” arm.

CF START is a Type A CTIMP, reflecting the low risk nature of the trial.

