8.3.3 Complications

A wide variety of CF complications may be recorded in the UK CF Registry from each encounter.. Examples of these include Allergic Bronchopulmonary Aspergillosis (ABPA), CF related diabetes (CFRD) and CF related liver disease (section 8.3.2). Participants will be monitored for adverse event data (complications) that meet the criteria of serious and possibly, probably or almost certainly related to flucloxacillin (section 10).

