10.2 Time Period for Safety Reporting

Safety reporting of Serious Adverse Reactions will be reported during the clinical trial from the date of randomisation until 48 months.

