10.2.1 Flowchart for Reporting Requirements of Adverse Events

For the purposes of CF START, adverse event data is drawn from the 'complications' tab of the UK CF Registry. This requires that encounter data be documented promptly on the UK CF Registry. Only complications that meet the criteria of serious and possibly, probably or almost certainly related to flucloxacillin will be expedited. Potential SARs should therefore be recorded on the UK CF Registry as soon as the centre becomes aware (within 24 hours).

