10.8.1 Non serious ARs/AEs (Complications)

All such events, whether related to flucloxacillin or not, should be recorded as a complication on the UK CF Registry.

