10.8.2 Serious ARs/SUSARs

SARs and SUSARs should be reported within 24 hours of the local site becoming aware of the event. The SAR form asks for the nature of event, date of onset, severity, corrective therapies given, outcome and causality. The responsible investigator should sign the causality of the event. Additional information should be submitted within 5 days if the reaction has not resolved at the time of reporting. Multiple events occurring at the same time should be recorded separately i.e. one SAR form per diagnosis.

The CTU will notify the MHRA and main REC of all SUSARs occurring during the trial according to the following timelines; fatal and life-threatening within 7 days of notification and non-life threatening within 15 days. All investigators will be informed of all SUSARs occurring throughout the trial. Local investigators should report any SUSARs as required locally. Responsibilities – Investigator

The Investigator is responsible for reporting all AEs that are observed or reported during the trial, regardless of their relationship to trial product.

All SARs must be reported immediately by the investigator to the CTU via a SAR form on the UK CF Registry.

- i. The minimum information required for reporting will appear as mandatory fields on the UK CF Registry.
- ii. The SAR form should be authorised by a designated investigator, a physician named on the 'signature list and delegation of responsibilities log' as responsible for reporting SARs and making trial related medical decisions. In the absence of the designated investigator the form should be completed and submitted by an alternative member of the research site trial team. As soon as possible thereafter the responsible investigator should check the SAR form, make amendments as appropriate, authorise and resubmit the form. The initial report shall be followed by detailed reports as appropriate.
- iii. Submit the SAR form through the registry (immediately, within 24 hours) to the CTU.
- iv. The UK CF Registry will send an email alert to the TC and CI to **notify** that a SAR form has been uploaded.
- v. The responsible investigator must **notify** their R&D department of the event (as per standard local governance procedures).
- vi. In the case of a SAR the participant must be followed up until clinical recovery is complete and laboratory results have returned to normal or until the event has stabilised. Follow-up may continue after completion of protocol treatment if necessary.

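### Serious, non-fatal events judged unrelated to flucloxacillin get contradictory reporting instructions, and the related-only rule would under-count harms of withholding prophylaxis

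*Protocol*

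**What the plan says.** Several parts of the Protocol set the scope of adverse event reporting.

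- 10.8, for either arm: "complications (AEs) will be reported for participants where the event is deemed serious and the causal relationship to flucloxacillin is assessed". The rest of the sentence requires the investigator to judge the event possibly, probably or almost certainly related.
- 8.3.3: "Participants will be monitored for adverse event data (complications) that meet the criteria of serious and possibly, probably or almost certainly related to flucloxacillin".
- 10.8.1, headed as covering non-serious events: "All such events, whether related to flucloxacillin or not, should be recorded as a complication on the UK CF Registry".
- 10.8.2, in the investigator responsibilities that follow the SAR and SUSAR procedure: "The Investigator is responsible for reporting all AEs that are observed or reported during the trial, regardless of their relationship to trial product".
- 10.2, on the reporting period: "Safety reporting of Serious Adverse Reactions will be reported during the clinical trial from the date of randomisation until 48 months".
- 10.2.1, on the source of the data: "adverse event data is drawn from the 'complications' tab of the UK CF Registry". On urgency: "Only complications that meet the criteria of serious and possibly, probably or almost certainly related to flucloxacillin will be expedited".

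For children allocated to no prophylaxis, 3.3 says that "the risks relate to earlier infection with SA and the potential impact of this on respiratory condition". The same section undertakes to assess the safety of both strategies.

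**The concern.** A site cannot tell from these sections whether to report a serious, non-fatal event that it considers unrelated to flucloxacillin. Sites that follow 10.8 will leave out events that sites following 10.8.2 will send in.

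The related-only rule also does not act equally on the two arms. The causality question is about flucloxacillin. A serious infection that arises because a child was not given flucloxacillin cannot ordinarily be called related to it, yet 3.3 places the risk of the Detect and Treat arm in exactly that area. The trial is unblinded (10.8.3), so a judgement made with knowledge of the allocation would decide which serious events are counted.

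At stake is the between-arm comparison of serious events, both for the IDSMC and in the final report. This has to be settled in the protocol because it governs what is collected. An analysis plan cannot tabulate events that were never recorded.

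**Working it through.** No arithmetic applies, and the protocol states no figure to reproduce. The check sets each class of event against each rule. Here *unrelated* means the two lowest categories of Table 4 (unrelated or unlikely).

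| Event | 8.3.3 and 10.8 | 10.8.1 | SAR/SUSAR procedure in 10.8.2 | General sentence in 10.8.2 |
|---|---|---|---|---|
| Serious, related | In scope | Not covered | SAR form within 24 hours | Report |
| Non-serious, related or not | Out of scope | Registry complication | Not covered | Report |
| Serious, unrelated, fatal | Out of scope | Not covered | Not covered | Report; 10.3.2 adds the withdrawal form within 7 days |
| Serious, unrelated, non-fatal | Out of scope | Not covered | Not covered | Report, with no route given |

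1. **Contradiction.** In the last row, 8.3.3 and 10.8 exclude the event and the general sentence in 10.8.2 includes it. No procedure in 10.8 says on which form, or where, it is recorded. Section 10.1 defines an SAE, but the reporting procedures are written for SARs and SUSARs.

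2. **Uneven effect.** Causality in 10.5 and 10.8 is assessed against flucloxacillin. Applying the rule in both arms does not make it neutral: harms of giving the drug can pass the test, while harms of not giving it ordinarily cannot.

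3. **What is collected regardless of causality.** Table 1 lists, for all participants to 48 months, inpatient stays and days, courses and days of extra antibiotics including intravenous ones, cultures positive for SA, and reports of ABPA, CFRD and CFRLD. Deaths not judged related reach the CTU under 10.3.2. Section 8.7 names more hospital days and more IV antibiotics as circumstances that may end the trial early.

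4. **What remains uncertain.** The admission and antibiotic outcomes are counts of stays, days and courses. They do not give a diagnosis, seriousness criterion and causality for each event. Serious events with neither admission nor death, such as the other important medical events in 10.1, may be missed. Section 11.3 rules out formal interim analysis of secondary outcomes and lists safety data for regular IDSMC review, so what counts as safety data affects oversight.

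**The case against.** The strongest reply is that the protocol intends two tiers: record everything, expedite only what is serious and related. Several places support this. Section 10.2.1 limits expediting, not recording. Section 10.4 grades severity whether or not an event is serious, Table 4 includes unrelated and unlikely categories, and 10.7 follows all adverse events. On this reading 10.8 is a loosely worded statement about the SAR form. The intention is plausible, but the text does not state it: 10.8 and 10.8.2 both speak of reporting, and 8.3.3 applies the same limit to monitoring.

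Second, the flowchart announced in 10.2.1 is not visible in the text available and might contain a branch for serious, unrelated events. That stands as a limit on the gap. It would not remove the conflict between the written sections.

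Third, 3.3 itself says that secondary outcomes will measure the respiratory impact of withholding prophylaxis. That also stands, and most serious infections that lead to admission would enter the inpatient counts. A reader might infer that harms of withholding prophylaxis go uncounted altogether; the outcomes in Table 1 and the rule on deaths show otherwise.

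A reader might also infer that almost no serious event in the Detect and Treat arm could qualify under 10.8. That is too strong. These children receive antibiotics for clinical indications (9.1), flucloxacillin is widely used for acute SA infection (3.3), and 8.5.2 foresees changes to Prevent and Treat. Related events can therefore occur in that arm.

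Finally, limiting expedited reporting to related events is not in itself an error, and the protocol presents this as a low-risk trial.

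**Conclusion.** The point holds in a limited form. Sections 8.3.3 and 10.8 conflict with 10.8.2 on which events are reported, and 10.8.1 does not close the gap because it covers only non-serious events. Serious, non-fatal events judged unrelated have contradictory instructions in the text available. If sites follow 10.8, serious-event counts will under-represent harms of withholding prophylaxis.

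The loss is of a serious-event listing with diagnosis by arm, and possibly of serious events without admission or death. It is not a loss of all information on such harms. Its size cannot be estimated from the protocol. Follow-up time in the Detect and Treat arm would describe exposure only and should not be read as a measure of the effect.

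The conclusion assumes that the flowchart in 10.2.1 does not settle the matter, and that investigators judge causality against the drug as 10.5 and 10.8 direct. The change is worth making because it is specific and improves the safety comparison between arms.

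**What to change.** Reconcile 8.3.3, 10.8, 10.8.1 and 10.8.2, and check the flowchart in 10.2.1 against the result. State that:

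- serious events in both arms are recorded on the existing Registry complications tab, with seriousness and causality, whatever the causality;
- these events are tabulated by randomised arm for the IDSMC and in the final report;
- 24-hour expedited reporting stays limited to SARs and SUSARs, as in 10.2.1.

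The cost is a wording amendment and some extra data entry at sites. The protocol does not describe the fields of the complications tab, so neither the amount of extra entry nor the need for a new seriousness field can be judged from it. No new visits or procedures are needed.

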10.8.1 Non serious ARs/AEs (Complications)

All such events, whether related to flucloxacillin or not, should be recorded as a complication on the UK CF Registry.

10.8.2 Serious ARs/SUSARs

SARs and SUSARs should be reported within 24 hours of the local site becoming aware of the event. The SAR form asks for the nature of event, date of onset, severity, corrective therapies given, outcome and causality. The responsible investigator should sign the causality of the event. Additional information should be submitted within 5 days if the reaction has not resolved at the time of reporting. Multiple events occurring at the same time should be recorded separately i.e. one SAR form per diagnosis.

The CTU will notify the MHRA and main REC of all SUSARs occurring during the trial according to the following timelines; fatal and life-threatening within 7 days of notification and non-life threatening within 15 days. All investigators will be informed of all SUSARs occurring throughout the trial. Local investigators should report any SUSARs as required locally. Responsibilities – Investigator

The Investigator is responsible for reporting all AEs that are observed or reported during the trial, regardless of their relationship to trial product.

All SARs must be reported immediately by the investigator to the CTU via a SAR form on the UK CF Registry.

- i. The minimum information required for reporting will appear as mandatory fields on the UK CF Registry.
- ii. The SAR form should be authorised by a designated investigator, a physician named on the 'signature list and delegation of responsibilities log' as responsible for reporting SARs and making trial related medical decisions. In the absence of the designated investigator the form should be completed and submitted by an alternative member of the research site trial team. As soon as possible thereafter the responsible investigator should check the SAR form, make amendments as appropriate, authorise and resubmit the form. The initial report shall be followed by detailed reports as appropriate.
- iii. Submit the SAR form through the registry (immediately, within 24 hours) to the CTU.
- iv. The UK CF Registry will send an email alert to the TC and CI to **notify** that a SAR form has been uploaded.
- v. The responsible investigator must **notify** their R&D department of the event (as per standard local governance procedures).
- vi. In the case of a SAR the participant must be followed up until clinical recovery is complete and laboratory results have returned to normal or until the event has stabilised. Follow-up may continue after completion of protocol treatment if necessary.
- vii. Follow-up information should be entered onto the UK CF Registry and submitted within 5 days if the reaction has not resolved at the time of initial report.
- viii. The participant **must** be identified by trial number, date of birth and initials only. The participant's name **should not** be used on any correspondence.

10.8.3 Maintenance of Blinding

This is an unblinded trial.

10.9 Responsibilities – CTU

The CTU is undertaking duties delegated by the trial co-sponsor, Alder Hey Children's NHS Foundation Trust, and is responsible for the reporting of SUSARs and other SARs to the regulatory authorities (MHRA and the research ethics committees) as follows:

- SUSARs which are fatal or life-threatening must be reported not later than 7 days after the CTU is first aware of the reaction. Any additional relevant information must be reported within a further 8 days.
- SUSARs that are not fatal or life-threatening must be reported within 15 days of the CTU first becoming aware of the reaction.
- A list of all SARs (expected and unexpected) must be reported annually.

It is recommended that the following safety issues should also be reported in an expedited fashion:

- An increase in the rate of occurrence or a qualitative change of an expected serious adverse reaction, which is judged to be clinically important;
- Post-trial SUSARs that occur after the participant has completed a clinical trial and are notified by the investigator to the sponsor;
- New events related to the conduct of the trial and likely to affect the safety of the participants, such as:

- a. A SAR which could be associated with the trial procedures and which could modify the conduct of the trial;
 - b. A significant hazard to the participant population, such as lack of efficacy of an IMP used for the treatment of a life-threatening disease;
 - c. A major safety finding from a newly completed animal trial (such as carcinogenicity).
 - d. Any anticipated end or temporary halt of a trial for safety reasons and conducted with the same IMP in another country by the same sponsor;
- Recommendations of the Data Monitoring Committee, if any, where relevant for the safety of the participants.

Staff at the CTU will liaise with the Chief Investigator (or designated other specified in the protocol) who will evaluate all SARs received for seriousness, expectedness and causality. Investigator reports of suspected SARs will be reviewed immediately and those that are SUSARs identified and reported to regulatory authorities and MREC. The causality assessment given by the Local Investigator at the hospital cannot be overruled and in the case of disagreement, both opinions will be provided with the report. The PIs at all institutions participating in the trial will be notified of any SUSARs.

Participant safety incidents that take place in the course of research should be reported to the National Reporting and Learning System (NRLS) by each participating NHS Trust in accordance with local reporting procedures.

10.9.1 Safety reports

Safety reports will be generated during the course of the trial which allows for monitoring of SAR reporting rates across sites. The CTU will send Developmental Safety Update Reports (DSURs) containing a list of all SARs to regulatory authorities and main REC. Any concerns raised by the IDSMC or inconsistencies noted at a given site may prompt additional training at sites, with the potential for the CTU to carry out site visits if there is suspicion of unreported AEs in participant case notes. Additional training will also be provided if unacceptable delay in safety reporting timelines. If any safety reports identify issues that have implications for the safety of trial participants, the PIs at all institutions participating in the trial will be notified.

